#### 3.3 Number of Subjects

Cases will be enrolled in this study until a total of 240 receive the Tritanium® Acetabular Shell. Half of these cases will use the X3® polyethylene insert alone as the bearing surface; the other half will use the MDMTM liner coupled with a compatible ADM/MDMTM X3® insert as the bearing surface. These treatment groups will not be separated into arms; instead, investigators will use their clinical judgement in determining the appropriate bearing for each case. If enrollment in one of the treatment groups begins to outpace that of the other, centers may be asked to enroll only those cases that are candidates for the bearing surface for which enrollment is lagging. Following this plan, cases will not be artificially placed into a treatment group to which they may not be best suited on the basis of the timing of their enrollment; consequently, there will be fewer opportunities for protocol deviations with regard to treatment.

Only the following ancillary devices may be used according to this study protocol:

- Stryker X3® polyethylene inserts (120 cases)
- Stryker MDMTM liners with ADM/MDMTM X3® polyethylene inserts (120 cases)
- Stryker LFIT™ CoCr heads or BIOLOX delta or alumina ceramic heads (in cases where the MDM™ liner is used, only 22.2 mm and 28 mm heads are permissible)
- Stryker Universal Adapter Sleeves (for use with BIOLOX delta universal ceramic heads)
- Compatible Stryker femoral stems
- Stryker Orthopaedics Torx Bone Screws

The Tritanium® Acetabular Shell is described in detail in Section 6 of this protocol, Device Description.

### 3.4 Estimated Study Duration

The enrollment period is estimated to be a maximum of 18 to 24 months; cases will be evaluated as per the evaluation schedule until each case reaches 10 years.

### 4 Eligibility

The following criteria will be used to distinguish patients eligible for enrollment into this study.

#### 4.1 Inclusion Criteria

- A. Patient has signed an IRB approved, study specific Informed Patient Consent Form.
- B. Patient is a male or non-pregnant female age 18 years or older at time of study device implantation.
- C. Patient has primary diagnosis of Non-Inflammatory Degenerative Joint Disease (NIDJD).
- D. Patient is a candidate for a primary cementless total hip replacement.
- E. Patient is willing and able to comply with postoperative scheduled clinical and radiographic evaluations and rehabilitation.

#### 4.2 Exclusion Criteria

- F. Patient has a Body Mass Index (BMI) ≥ 40.
- G. Patient has an active or suspected latent infection in or about the affected hip joint at time of study device implantation.
- H. Patient has a neuromuscular or neurosensory deficiency, which limits the ability to evaluate the safety and efficacy of the device.
- Patient is diagnosed with a systemic disease (e.g. Lupus Erythematosus) or a metabolic disorder (e.g. Paget's disease) leading to progressive bone deterioration.
- J. Patient is immunologically suppressed or receiving steroids in excess of normal physiological requirements (e.g. > 30 days).
- K. Patient requires revision surgery of a previously implanted total hip replacement or hip fusion to the affected joint.
- L. Patient has a known sensitivity to device materials.
- M. Patient is a prisoner.

### 5 Subject Enrollment

#### 5.1 Treatment Assignment

All subjects will receive the Tritanium® Acetabular Shell. Half of the cases will use the X3® polyethylene insert alone as the bearing surface; the other half will use the MDMTM liner coupled with a compatible ADM/MDMTM X3® insert as the bearing surface. Treatment assignment will be made based upon the clinical judgment of each investigator and enrollment into each treatment group will be monitored by Stryker to ensure equal distribution between the two groups.

#### 5.2 Randomization

The study will enroll under a non-randomized study design.

### **6 Device Description**

#### 6.1 Study Device

The Tritanium® Acetabular Shell has been cleared for use in the United States; therefore, this study is considered a post-market assessment. All cases in this study will receive the Tritanium® Acetabular Shell. Half of the cases will use the X3® polyethylene insert alone as the bearing surface; the other half will use the MDMTM liner coupled with a compatible ADM/MDMTM X3® insert as the bearing surface. Only the following **Stryker compatible** ancillary devices may be used, according to this study protocol:

- Stryker X3® polyethylene inserts (120 cases)
- Stryker MDMTM liners with ADM/MDMTM X3® polyethylene inserts (120 cases)
- Stryker LFITTM CoCr heads or BIOLOX *delta* and alumina ceramic heads (in cases where the MDMTM liner is used, only 22.2 mm and 28 mm heads are permissible)
- Stryker Universal Adapter Sleeves (for use with BIOLOX delta universal ceramic heads)
- Compatible Stryker femoral stems
- Stryker Orthopaedics Torx Bone Screws

#### **Device Description:**

The Tritanium® Acetabular Shell consists of a porous coated hemispherical cup available in solid back and cluster-hole designs, and is similar to other acetabular shells currently distributed. It is intended for cementless application and is designed for use with currently available Stryker MDMTM liners and polyethylene inserts. A description of the Tritanium® Acetabular Shell and compatible liner/insert/head combinations follows. Appendix B gives an overview of all protocol-specified components.

The X3® Polyethylene Insert is the next generation of highly cross-linked UHMWPE with excellent mechanical and fatigue properties. X3® polyethylene is a highly cross-linked polyethylene manufactured through a proprietary, step-wise sequential irradiation and annealing process through which the polyethylene receives 30 kiloGrays of gamma radiation and is then annealed below melting point to promote cross-linking. This highly cross-linked polyethylene has shown reduction in polyethylene wear with approximately the same mechanical properties of standard polyethylene.

The Modular Dual Mobility (MDM™) liner, cleared for use under FDA 510(k) K103233, features a highly polished cobalt chrome (CoCr) liner with a Trident® locking mechanism which will allow for compatibility with the Tritanium® acetabular cup system. The X3® polyethylene insert will articulate within the inner surface of the highly polished cobalt chrome liner. The polyethylene insert and 22.2 mm or 28 mm femoral head will combine to create the dual mobility bearing. The MDM™liner is available in sizes from 36 mm through 58 mm and is compatible with ADM/MDM™ X3® Inserts. The MDM™ system is designed to provide stability through the use of large diameter dual mobility liners and advanced fixation through the use of ancillary fixation and Tritanium® acetabular shells.

#### Tritanium® Acetabular Shell:

The catalog numbers for the Tritanium® Acetabular Shell permissible according to this study protocol will be in the following format, where 'XXX' varies by size:

500-03-XXX (solid back) 502-03-XXX (cluster hole)

#### X3® Polyethylene insert:

The catalog numbers for the X3® polyethylene inserts permissible according to this study protocol will be in the following format, where 'XXX' varies by size:

623-00-XXX (0°) 623-10-XXX (10°)

Table 3. Tritanium® Acetabular Shell/Liner/Head Compatibility

		Shell Size, Liner Alpha Code and Liner Thickness (mm)							
Tritanium ® Acetabular Shell		44	46	48	50, 52	54, 56	58, 60	62, 64	66
X3 ® Liner Alpha Code		Α	В	С	D	E	F	G	Н
Anatomic Heads	44mm						3.8	5.4	7.1
	40mm					3.8	5.8	7.4	9.1
	36mm				3.9	5.9	7.9	9.4	11.2
Femoral Heads	32mm		3.9	4.9	5.9	7.9	9.9	11.4	13.2
	28mm	4.9	5.9	6.9	7.9	9.9	11.9	13.4	15.2
	26mm			7.9	8.9	10.9	12.9	14.4	16.2
	22mm	7.8	8.8	9.8	10.8	12.8	14.8	16.3	18.1

#### **MDM™** Liner:

The catalog numbers for the MDMTM liner permissible according to this study protocol will be in the following format, where 'XXX' varies by size:

626-00-XXX

#### **ADM/MDM™ X3® Polyethylene Insert:**

The catalog numbers for the dual mobility polyethylene inserts permissible with the MDM™ Liner according to the study protocol will be in the following format, where 'XXX' varies by size:

1236-2-XXX

Table 4. MDM™ Liner/Insert/Head Compatibility Chart

MDM™ Liner	MDM™ Liner Trial	ADM/MDM™ X3 ® Insert	ADM/MDM™ Insert Trial	Required Femoral Head Size (mm)
626-00-36C	3200-36C	1236-2-242	1235-0-242	22.2mm
626-00-38D	3200-38D	1236-2-244	1235-0-244	22.2mm
626-00-42E	3200-42E	1236-2-848	1235-0-848	28mm
626-00-46F	3200-46F	1236-2-852	1235-0-852	28mm
626-00-48G	3200-48G	1236-2-854	1235-0-854	28mm
626-00-52H	3200-52H	1236-2-858	1235-0-858	28mm
626-00-541	3200-541	1236-2-860	1235-0-860	28mm
626-00-58J	3200-58J	1236-2-864	1235-0-864	28mm

Table 5. MDM™ Liner/Insert/Tritanium® Shell Compatibility Chart

Shell Size (mm), Liner Alpha Code								
Tritanium Hemispherical Shell	48	50,52	54,56	58,60	62,64	66		
Liner Alpha Code	С	D	Е	F	G	Н		
MDM CoCr Liner	36C	38D	42E	46F	48G	52H		
Poly Insert OD (mm)	36	38	42	46	48	52		
Poly Insert ID (mm)	22.2	22.2	28	28	28	28		
Nominal Poly Thickness (mm)		7.7	6.8	8.8	9.8	11.8		

#### **Ancillary Devices:**

Only compatible Stryker femoral stems, Stryker LFITTM CoCr or BIOLOX *delta* or alumina ceramic heads, standard X3® inserts and MDMTM liners with ADM/MDMTM X3® inserts may be used as ancillary devices according to this study protocol.

Tritanium® Primary Acetabular Shell Study Stryker Orthopaedics Clinical Study Protocol Version 3.0

The patenteda sequential irradiation and annealing manufacturing process for X3® offers increased wear resistance b and virtually eliminates free radicalsc while preserving mechanical propertiesd,e,f,g. X3® is irradiated by 3 MRads gamma radiation and annealed (heated below melting temperature) three times for a total cumulative dose of 9 MRads.

#### 6.2 Device Retrieval Process

Stryker Orthopaedics will retrieve any Stryker component removed along with adjacent tissues (if applicable) for analysis to help characterize potential device-related complications. In the event that any Stryker component is removed from a study subject, the outlined procedure should be followed.

<sup>a U.S. Patent # 6,174,934 6,372,814 6,664,308 6,818,020 7,517,919

<sup>bStryker Orthopaedics Trident Acetabular Inserts made of X3 UHMWPE (unsterilized), 721-00-32E, show a 97% reduction in volumetric wear rate versus the same insert fabricated from N 2 \Vac gamma sterilized UHMWPE, 620-00-32E. The insert tested was 7.5 mm thick with an inner diameter of 32 mm. Testing was conducted under multi-axial hip joint simulation for 5 million cycles using a 32 mm CoCr articulating counterface and calf serum lubricant. X3 UHMWPE Trident acetabular inserts showed a net weight gain due to fluid absorption phenomena but yielded a positive slope and wear rate in linear regression analysis. Volumetric wear rates were 46.39  $\pm$  11.42 mm³ /106 cycles for N2 \Vac gamma sterilized UHMWPE inserts and 1.35  $\pm$  0.68 mm³ /106 cycles for X3 UHMWPE (unsterilized) Trident Acetabular Inserts. Although in-vitro hip wear simulation methods have not been shown to quantitatively predict clinical wear performance, the current model has been able to reproduce correct wear resistance rankings for some materials with documented clinical results. IV, V, VI

iv] Wang A, et al. Tribology International, Vol. 31, No. 1-3:17-33, 1998.

v] Essner A. et al. 44th Annual Meeting, ORS, New Orleans, Mar. 16-19, 1998:774.

vi] Essner A. et al. 47th Annual Meeting, ORS, San Francisco, Feb. 25-28, 2001:1007

 $^{\rm c}$  X3 UHMWPE virtually eliminates free radicals, as measured by Electron Spin Resonance (ESR). A very low (noise level, near instrument detection limit) concentration of residual free radicals was detected in the X3 UHMWPE. A 99% reduction of free radicals (14  $\pm$  2 x 10^14 spins/gram versus 1550  $\pm$  32 x 10^14 spins/gram) was found when compared to N2Vac gamma sterilized UHMWPE.

 $^{m d}$  X3 UHMWPE maintains mechanical properties after accelerated oxidative aging. No statistical difference was found for Tensile Yield Strength, Ultimate Tensile Strength and Elongation as measured per ASTM D638 before and after exposure to ASTM F2003 accelerated aging (5 Atmospheres (ATM) of oxygen at 70°C for 14 days). Tensile Yield Strength was 23.5  $\pm$  0.3 MPa and 23.6  $\pm$  0.2 MPa, Ultimate Tensile Strength was 56.7  $\pm$  2.1 MPa and 56.3  $\pm$  2.3 MPa and Elongation was 267  $\pm$  7% and 266  $\pm$  9% before and after accelerated oxidative aging, respectively.

 $^{\rm c}$  X3 UHMWPE resists the effects of oxidation. No statistical difference was found for Tensile Yield Strength, Ultimate Tensile Strength, Elongation, Crystallinity and Density as measured per ASTM D638, D3417 and D1505 before and after ASTM F2003 accelerated aging (5 ATM of oxygen at 70°C for 14 days). Tensile Yield Strength was 23.5  $\pm$  0.3 MPa and 23.6  $\pm$  0.2 MPa, Ultimate Tensile Strength was 56.7  $\pm$  2.1 MPa and 56.3  $\pm$  2.3 MPa, Elongation was 267  $\pm$  7% and 266  $\pm$  9%, Crystallinity was 61.7  $\pm$  0.6% and 61.0  $\pm$  0.5%, and Density was 939.2  $\pm$  0.1 kg/m3 and 939.2  $\pm$  0.2 kg/m3 before and after accelerated oxidative aging, respectively.

f "Improved Strength of Cross-linked UHMWPE Without Compromising Oxidation/Fatigue Resistance and Wear", Yau SS; Wang A, Lovell T. 2007 Combined ORS Poster #496.

<sup>g "Wear, oxidation and mechanical properties of a sequentially irradiated and annealed UHMWPE in total joint replacement", A.Wang, H.Zeng, S-S Yau, A. Essner, M. Manley and J. Dumbleton, Journal of Physics, D:Appl: Phys 39 (2006).

- 1. When revision of a study subject is scheduled, the study coordinator (SC) should contact the Clinical Study Manager (CSM) or Clinical Study Associate (CSA) assigned to the project, as soon as possible.
- 2. The CSM or CSA will send a retrieval container to the SC.
- 3. After the device is explanted, the SC or an identified Stryker field representative will retrieve the device and place it in the retrieval container.
- 4. The SC, an identified field representative or the CSM/CSA will complete a Product Experience Report (PER).
- 5. If not completed by the CSM or CSA, the PER should be faxed to Stryker Product Surveillance at [contact], as well as to Stryker Clinical Research at [contact].
- 6. The PER should be attached to the retrieval container and sent to Product Surveillance.

  A de-identified operative report should be included, when available.
- 7. The CSM or CSA will follow up with Product Surveillance to obtain a PER number.
- 8. A summary of results will be provided to the investigator upon his/her request.

### 7 Evaluations

#### 7.1 Preoperative Visit

During the preoperative visit, patients that are possible candidates for this study will be screened to determine if they meet the inclusion/exclusion criteria. If the patient is a candidate, the investigator will propose participation in the study to the patient, according to GCP guidelines. Patients must sign an IRB approved study consent form prior to participating in any study related activities. Consent must be obtained within four months of surgery.

Once the subject has been consented, preoperative data will be collected including: demographics, medical history, HHS, AP hip, AP pelvis and lateral radiographs, SF-12, LEAS and EQ-5D.

All preoperative data must be collected within 4 months of the scheduled date of surgery, with the exception of radiographs, acceptable within 1 year of the scheduled date of surgery. All information collected preoperatively will be used to quantify the sample population and compare postoperative progress.

### 7.2 Surgery

Surgical details will be collected from the operative notes and at the time of surgery.

#### 7.3 6-week Visit

During the 6-week visit (± 2 weeks), the following evaluations will be collected: HHS, SF-12, LEAS, EQ-5D, AP hip, AP pelvis and lateral radiographs.

#### 7.4 Annual Follow-up Visits

Clinical data will be collected via office visit by the investigator at the following annual postoperative intervals: 1-year, 3-year and 5-year. Tools for postoperative evaluation will be the HHS, AP hip, AP pelvis and lateral radiographs.

Patient outcomes data will also be collected via patient questionnaires. At each of the 1-year, 3-year and 5-year follow-up visits, the SF-12, LEAS and EQ-5D are required. These same questionnaires are also required at 2-year and 4-year intervals, and may be completed during an office visit or sent to the subject to be completed, initialed and dated and returned to the investigative site.

All clinical data, radiographs, and patient outcomes data must be collected within  $\pm$  2 months of the 1-year and 2-year anniversary dates. For remaining annual time points, the window expands to  $\pm$  3 months of the 3-year anniversary date and  $\pm$  4 months of the 4-year and 5-year anniversary dates.

The initial phase of the study will continue for 5 years after surgery and include collection of the previously described radiographs, HHS, and SF-12, LEAS and EQ-5D patient questionnaires. In the second phase of the study, all subjects will complete a brief satisfaction questionnaire annually at the 6-year, 7-year, 8-year, 9-year and 10-year follow-up intervals. This form may be completed by the SC during a patient telephone interview, or by the patient either at home or during a clinic visit. The questionnaire will be used to obtain the following information, at a minimum:

- Patient satisfaction with the hip replacement
- Presence of any pain in the study hip
- Any surgeries performed on the study hip

The questionnaire will also provide information on any revisions and enable calculation of the Kaplan-Meier survival curve necessary to meet the primary endpoint of the study.

Additionally, at investigational sites that choose to continue collecting clinical and radiographic data during the second phase of the study, subjects will be evaluated again at 7 and 10 years after surgery.

### **8 Adverse Events**

### 8.1 Reporting of Adverse Events

The AE reporting requirements for this study are as follows:

- All AEs that meet the definition of serious, excluding elective procedures
- All AEs related to the operative site, regardless of seriousness

Elective procedures meeting the definition of an SAE do not need to be reported as AEs according to this study protocol. Examples of such elective procedures include, but **are not limited to**, the following commonly seen events:

- Contralateral THR
- Total Knee Replacement
- Rotator Cuff Surgery
- Cataract Surgery

[figure not shown]
Such events will not be captured on the AE electronic Case Report Form (eCRF) but rather will be captured on the postoperative functional evaluation at the 6-week, 1-year, 3-year, and 5-year, time points. Additional events of this nature will be captured on the 7-year and 10-year functional evaluations if the investigator chooses to bring subjects in for these optional visits. On these functional evaluations, investigators and SCs will be prompted to question subjects as to whether they have seen a doctor for any reason, been hospitalized for any reason or have a current impediment to their function.

Additionally, SCs will be responsible for following up with the subjects regarding any questionable responses received on the satisfaction questionnaire administered in postoperative years 6 through 10. If it is determined upon this further investigation that a protocol-defined adverse event has occurred, the SC will be responsible for completing an AE eCRF and submitting the event to the sponsor, and reporting to the IRB as required.

The following decision tree facilitates identification of AEs for which reporting is required under this study protocol:

Figure 1

Adverse Event Decision Tree

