#### Adverse Event Reporting Period

The study period during which AEs must be reported is normally defined as the period from the initiation of any study procedures to the end of the study treatment follow-up. The start of study procedures is considered to be the point of consent. Any AEs which fit the protocol defined reportable events must be reported from the time of consent until study completion.

At each contact with the subject the investigator must seek information on AEs by specific questioning and, as appropriate, by examination. Information on protocol defined AEs should be recorded immediately in the source document and also in the appropriate AE module of the eCRF. All clearly related signs, symptoms and abnormal diagnostic procedure results should be recorded in the source document and grouped under one diagnosis as appropriate. The clinical course of each event should be followed until resolution or until it is determined at the end of the study that the AE will not resolve.

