#### Serious Adverse Event

A **SAE** meets one or more of the following definitions:

- Resulted in in-patient hospitalization
- Resulted in prolonged existing hospitalization
- Resulted in persistent or significant disability/incapacity
- Resulted in permanent impairment of a body function or permanent damage to a body structure
- Necessitated medical or surgical intervention to preclude permanent impairment of a body function or permanent damage to a body structure
- Was a life-threatening situation
- Resulted in patient death

Elective procedures meeting the definition of an SAE do not need to be reported as AEs according to this study protocol.

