## Stryker® Orthopaedics

## Tritanium® Primary Acetabular Shell POST-OP FUNCTIONAL EVALUATION

IV.	EVENTS	

K. Have there been any protocol defined Adverse Events since the last visit?	Yes*	No lete an AE form for each.
USE THIS SECTION TO REPORT MEDICAL EVENTS OTHER THAN PROTOCOL DEFIN	ED ADVERSE	EVENTS.
L. Has the subject seen a doctor for any medical event since the last visit?  *If Yes, specify:	○ Yes*	○ No
M. Has the subject been hospitalized for any elective surgery since the last visit	? ∩ Yes*	○ No
*If Yes, specify (check all that apply)		
*Provide Details		
N. Is anything currently affecting the subject's function? Yes* No *If Yes, specify:		
. COMMENTS		
Reason for Save Verification / Confirmation Method		

Stryker®

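### Section 8.1 promises a question on admission to hospital for any reason, but the draft functional evaluation form asks only about elective surgery, so unplanned admissions are reached only indirectly

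*Combined protocol and SAP*

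**What the plan says.** Section 8.1 makes two classes of event reportable: "All AEs that meet the definition of serious, excluding elective procedures", and every operative-site AE whatever its seriousness. In the Section 8.2 definition of a serious adverse event, the first criterion is "Resulted in in-patient hospitalization". Elective procedures that would meet the definition are kept off the AE form. They are recorded on the postoperative functional evaluation at 6 weeks and 1, 3 and 5 years, and at 7 and 10 years where a site holds the optional visits.

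Section 8.1 adds that on these evaluations staff will be prompted to ask subjects "whether they have seen a doctor for any reason, been hospitalized for any reason or have a current impediment to their function". Under the Adverse Event Reporting Period heading it also sets a general duty: "At each contact with the subject the investigator must seek information on AEs by specific questioning and, as appropriate, by examination".

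The Events part of the Post-Op Functional Evaluation form (Appendix E) opens with item K, "Have there been any protocol defined Adverse Events since the last visit", and calls for an AE form for each one. A heading follows, "USE THIS SECTION TO REPORT MEDICAL EVENTS OTHER THAN PROTOCOL"-defined AEs. Below it come item L, "Has the subject seen a doctor for any medical event since the last visit", item M, "Has the subject been hospitalized for any elective surgery since the last visit", and item N, on anything now affecting function. Section 11.1 describes the Appendix E forms as draft specifications.

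**The concern.** Items L, M and N follow the three prompts of Section 8.1 in the same order. L and N keep the breadth of the text. M alone is narrowed, and to the one class of admission that the protocol does not want reported as an AE. No item on the form names an unplanned admission.

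This matters most for events away from the operative site, such as cardiac or respiratory events. An operative-site event is reportable however mild. Any other event is reportable only if it is serious, and an admission is often what makes it so. A plain question about admissions is how staff would learn of an event treated at another hospital.

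What is at stake is the completeness of the serious adverse event data. Section 2.2 sets these against the historical control and published data, and Section 9.2.2 summarises them as rates with 95% confidence intervals.

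**Working it through.** No arithmetic applies to the conflict itself. The check sets the text beside the form.

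**1. Promise against form**

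| Prompt in Section 8.1 | Item on the form | Match |
|---|---|---|
| Seen a doctor, whatever the cause | L: any medical event | Broadly yes |
| Admitted to hospital, whatever the cause | M: elective surgery only | No |
| Current impediment to function | N: anything affecting function now | Yes |

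**2. Where an AE with an unplanned admission should go.** It meets an SAE criterion in Section 8.2 and is not an elective procedure, so under Section 8.1 it is a protocol-defined AE. On the form it belongs under item K and needs an AE form.

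**3. What would bring it to light**

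- *Item K* asks whether protocol-defined AEs have occurred. To answer yes, staff must already know of the event and recognise that it meets the definition. The item classifies an event; it does not put a plain question to the subject.
- *Item L* would pick up many admissions if the subject answers fully. But it sits under the heading for other events. In the text available its only instruction is to specify, with no direction to an AE form.
- *The general duty* in Section 8.1 calls for specific questioning at each contact but supplies no wording. The specific hospital question that Section 8.1 describes is the one the form lacks.

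So there are routes, and all of them are indirect.

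**4. Interval covered.** Required functional evaluations fall at 6 weeks and 1, 3 and 5 years. The two longest nominal gaps are 3 − 1 = 2 years and 5 − 3 = 2 years. At 2 and 4 years Section 7.4 requires only the SF-12, LEAS and EQ-5D, which may be completed away from the clinic. None of the three, as reproduced in Appendix E, asks about admissions.

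**5. Size.** Let N be the number of subjects, r the proportion with an unplanned admission, and d the gain in capture from a direct question. The number of subjects missed is N × r × d. The documents give N = 240 cases but neither r nor d, so the loss cannot be computed from them.

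**6. Primary endpoint.** Revision or removal of the shell has its own routes: 24-hour sponsor notification (Section 8.3), the treatment section of the AE form and the Study Termination form. None depends on item M.

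**The case against.** The strongest reply is that unplanned admissions do have a prompt. Item K stands first in the Events section, covers every non-elective SAE and leads to an AE form, which itself lists systemic events and has a box for inpatient hospitalization. Item L is broad, and a subject who was admitted has seen a doctor. The Section 8.1 sentence also closes a paragraph about elective procedures, which explains why M was worded as it was. Section 13.1 adds monitoring at least yearly against source documents.

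The status of the form is also uncertain. Appendix E is a draft, the form carries a date of 08Feb2010 while the protocol is Version 3.0 of 8/24/2020, and completion instructions are in a separate guide (Section 11.4). The AE decision tree and the answer options under item M are not visible in the text available.

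Much of this stands. A reader might infer that the form gives no prompt at all for unplanned admissions; items K and L and the general duty show otherwise. A reader might also infer a measurable shortfall that flatters the device. For example, assuming r = 20% to 30% and d = 15 points gives 240 × 0.20 × 0.15 = 7.2 to 240 × 0.30 × 0.15 = 10.8 subjects, or 3.0 to 4.5 percentage points. Both inputs are invented, and the result falls to zero as d does, which is possible if K and L work well. The direction is unproven too. The synopsis says the control study's intervals and data closely match this one, but not how it asked about serious events, so under-capture could affect both sides.

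What the reply does not do is reconcile the two texts. The paragraph's context explains item M, yet Section 8.1 still describes a question without the elective limit. Monitors comparing charts at the study center need not see an admission elsewhere. A draft specification attached to the current protocol is the right place to correct the mismatch.

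**Conclusion.** The concern holds in limited form. Section 8.1 and item M conflict: the text describes a question on any admission, and the form asks only about elective surgery. As a result, AEs with unplanned admissions depend on staff recognition under item K, on an item L answer being carried over to an AE form, and on a general duty to ask. Some could be missed over intervals of nominally two years.

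The size of any loss and its effect on the comparison with the historical control cannot be estimated from the documents. The primary endpoint is untouched. The conclusion assumes that the form in use resembles the Appendix E draft; if the final eCRF already carries the broader question, only the appendix is out of date. Classification: wrong as written, because form and protocol text conflict; severity minor.

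**What to change.** Align the form with Section 8.1. Reword item M to ask whether the subject has been admitted to hospital for any reason since the previous visit, with two branches:

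- elective: give details on this form, as now;
- not elective: complete an AE form.

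Move the item out of the block reserved for other events, or amend that heading, so that the second branch does not contradict it. Use the same wording wherever the form is completed: 6 weeks, 1, 3 and 5 years, and the optional 7- and 10-year visits.

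The cost is one eCRF item changed and a few more AE forms, with no added visit or procedure. Narrowing Section 8.1 to match the form would also remove the conflict, but it would give up the direct question that the protocol already commits to.
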